13.3 Anticipated Adverse Events and Procedure Effects

These refer to AEs related to acute heart failure.

- Acute coronary syndrome (unstable angina, non ST elevation myocardial infarction, ST elevation myocardial infarct)
- Arrhythmias and sudden cardiac death
- Venous thrombosis

- Cerebrovascular events (stroke or transient ischemic attacks)
- Worsening heart failure or heart failure refractory to therapy requiring inotropes or mechanical support
- Presyncope and syncope
- Acute kidney injury defined as a rise in creatinine > 0.3 mg/dL over 48 hours, or progressive loss of renal function over time.

13.4 Device Adverse Events

If the pump falls off during drug infusion or if the needle appears before pump placement there is a risk of needle stick. In this scenario, the pump will need to be handled carefully. Device adverse reactions could include local reaction/skin irritation or redness, allergic reaction to the adhesive agent, and rarely scarring.

13.5 Pre Specified Adverse Events

Hyperkalemia defined as $K > 5.5$ meq/L

Hypokalemia, defined as $K < 3.0$ meq/ml

Hypomagnesemia, defined as $Mg < 1.5$ mg/dl

Worsening kidney function (50% increase in baseline creatinine level)

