6.2 EXCLUSION CRITERIA

- ACC/AHA Stage D heart failure or patients requiring IV inotrope therapy.
- Massive volume overload (e.g., >20 lbs. of estimated fluid weight) or anasarca.
- Suspected high risk clinical instability with outpatient treatment.
- Pregnant females or women of child-bearing age who are not willing to use an adequate form of contraception.
- Chronic Obstructive Pulmonary Disease (COPD) moderate or worse: FEV1/FCV ratio <0.7 and FEV1 <60 percent predicted.
- Rapid atrial fibrillation (AF) (HR >100 b/min).
- Hypoxia (resting O₂ saturation $<90\%$).
- Hypotension (systolic blood pressure (SBP) BP < 90 mmHg).
- Uncontrolled diabetes mellitus (DM) (admission glucose levels > 300 mg/dL).
- Advanced renal disease (eGFR < 30 mL/min/1.73m²).
- Acute coronary syndrome.
- Serum potassium (K⁺) <3.2 mmol/L or > 5.5 mmol/L.
- On experimental medication or currently participating in an interventional cardiovascular research study, other than an observational or registry study.
- Having received intravenous furosemide within 24 hours prior to enrollment.
- Urinary tract abnormality or disorder interfering with urination.
- Allergy to the active and inactive ingredients of the study medication.
- Inability to comply with study requirements.
- Ongoing substance abuse.

- Concern that the current episode of decompensation was precipitated by a serious medical condition which may require additional evaluation or treatment.
- Dementia

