9.5 Electrolyte Correction

At the clinic, prior to the start of therapy –a basic metabolic panel, pro-BNP, hemoglobin and hematocrit, and magnesium level will be drawn STAT to ensure that the results are back within 2 hours. Electrolytes will be replenished in accordance with established protocols (Tables 1 and 2)¹⁰. The same protocol will be utilized for electrolyte imbalances correction during the follow up visits by the visiting home nurse.

Serum Creatinine (mg/dL)	Serum Potassium Level (mEq/L)				
	< 3.1	3.1-3.3	3.4-3.6	3.7-4.0	> 4.0
< 2.0	40 mEq then 40 mEq	40 mEq then 20 mEq	40 mEq	20 mEq	-
2.0-2.8	40 mEq then	20 mEq then	20 mEq	-	-

	20 mEq	10 mEq			
> 2.8	30 mEq	20 mEq	10 mEq	-	-

* If the serum potassium is < 3 mEq/L or > 5.5 mEq/L, additional monitoring should occur within 24 hours.

Serum Creatinine (mg/dL)	Magnesium Level (mEq/L)			
	< 1.0	1.0-1.5	1.6-1.9	> 1.9
< 2.0	3 gm	2 gm	1 gm	-
≥ 2.0	2 gm	1 gm	-	-

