13 PARTICIPANT SAFETY AND ADVERSE EVENTS

Adverse Events

An adverse event (AE) is any unfavorable or unintended medical occurrence associated with the use of an investigational product (IP). This does not necessarily imply causality. Pre-existing conditions would be reported as AEs if the frequency, intensity, or character of the pre-existing condition worsens during the course of the study. Conditions detected after use of the IP are AE, though they might have prior existence. Laboratory or functional test abnormalities that meet the criteria for AEs are those that are associated with clinical signs or those whose clinical symptoms require medical intervention, and or which require the IP to be discontinued. When the patient withdraws from the study

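### Section 13.5 gives the hypokalemia threshold per millilitre instead of per litre, so every potassium result would meet it as written

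*Combined protocol and SAP*

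**What the plan says.** Section 13.5 pre-specifies four laboratory adverse events. The two potassium lines are adjacent: "Hyperkalemia defined as $K > 5.5$ meq/L", then "Hypokalemia, defined as $K < 3.0$ meq/ml". The other two are a magnesium cut in mg/dl and a relative rise in creatinine from baseline.

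Potassium limits appear in two other parts of the protocol:

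- **Section 9.5 (Electrolyte Correction).** The replacement table is in mEq/L, and its footnote reads "If the serum potassium is < 3 mEq/L or > 5.5 mEq/L, additional monitoring should occur within 24 hours".
- **Section 6.2 and the synopsis.** Patients are excluded if serum potassium is "<3.2 mmol/L or > 5.5 mmol/L".

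Sections 10.2 and 14 say that safety will be reported through the incidence of adverse events. Section 13 also has a general rule for laboratory findings: "Laboratory or functional test abnormalities that meet the criteria for AEs are those that are associated with clinical signs", or that need medical intervention or discontinuation of the product.

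**The concern.** The two potassium lines in Section 13.5 concern the same analyte but use different units, and the second is not physiologically possible as a lower limit. A cut in mEq per millilitre is a thousand times the same number in mEq per litre. A value of 3.0 on that scale lies far above any serum potassium, so a below-threshold rule would catch every sample.

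At stake is the definition of a safety event that matters for this product. Section 11 names electrolyte imbalance as a risk of diuresis, and potassium is measured by the visiting nurse on treatment days (Section 9.2) and again at the follow-up visits (Sections 9.3 and 9.4). Section 13.5 is the only place that defines hypokalemia as a pre-specified adverse event. Anyone who tabulates the event must either apply a rule that every patient meets or depart from the text without a documented basis.

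**Working it through.** The threshold does not come from a formula, so there is no plan figure to reproduce. The check is a unit conversion followed by a comparison with the protocol's other potassium limits.

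**Inputs**

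- Hypokalemia event: K below 3.0 meq/ml (Section 13.5)
- Hyperkalemia event: K above 5.5 meq/L (Section 13.5)
- Extra-monitoring trigger: K below 3 or above 5.5 mEq/L (Section 9.5 footnote)
- Eligible baseline range: 3.2 to 5.5 mmol/L (Section 6.2)
- Planned enrolment: 60 (synopsis)

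**Step 1. Convert the written cut.** 3.0 mEq/mL × 1000 mL/L = 3000 mEq/L.

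**Step 2. Compare with Section 9.5.** 3000 / 3 = 1000. The number is the same and only the unit differs.

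**Step 3. Compare with eligibility.** Potassium is monovalent, so 1 mmol/L = 1 mEq/L and the eligible range is 3.2 to 5.5 mEq/L (0.0032 to 0.0055 mEq/mL).

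- Against the upper limit: 3000 / 5.5 ≈ 545
- Against the lower limit: 3000 / 3.2 = 937.5

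Every eligible baseline value is therefore below the written cut, and 60 of 60 planned patients meet the criterion before treatment.

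**Step 4. Check the two potassium lines together.** Hyperkalemia starts above 5.5 mEq/L and the written hypokalemia rule covers everything below 3000 mEq/L. Any realistic hyperkalemia result satisfies both, although the two events should exclude each other.

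**Step 5. Repeat with mEq/L.** The cut becomes 3.0 mEq/L, which matches the Section 9.5 trigger. It lies 3.2 − 3.0 = 0.2 mEq/L below the eligibility floor, so 0 of 60 patients who satisfy the potassium criterion meet it at baseline. It no longer overlaps with hyperkalemia.

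**Step 6. Look for knock-on effects.** The only sample-size statement, in Section 14, concerns 59 evaluable subjects and a 5% event incidence. The probability of seeing at least one such event is 1 − 0.95^59 = 0.9515, which agrees with the stated 95% and does not use the potassium threshold.

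**The case against.** The strongest reply is that this is a typing slip that nobody would follow. The intended value stands in the Section 9.5 footnote, with the same pair of cuts. Section 13.5 attaches no action to the value, while potassium replacement and repeat monitoring are governed by Section 9.5, where the units are right. The analysis is descriptive, and no test, stopping rule or dose decision uses the line. The ratios above all restate one unit slip and do not measure an effect on the trial.

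The reply also points to Section 13. Pre-existing conditions count as adverse events only if they worsen, and laboratory abnormalities count only with clinical signs, intervention or discontinuation. On that reading a baseline potassium value would not be recorded as an adverse event even under the wrong unit.

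Most of this stands, and it limits the severity. The 60 of 60 figure shows how many patients meet the numerical criterion. It does not forecast the reported incidence, and the protocol does not spell out how Section 13 and the list in Section 13.5 work together. A programmer could also infer the right cut from Section 9.5. None of this makes the written definition correct: an analyst who applies the sensible value is correcting the protocol, not following it.

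A PDF-reading fault cannot be wholly excluded, since the text was machine-read. It is unlikely, because the line directly above was read with the litre unit and this fault would have had to add a letter.

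**Conclusion.** The point holds and is minor. One of the four laboratory thresholds in Section 13.5 carries the wrong unit, which overstates the cut by a factor of 1000. Applied literally, it classifies every potassium result as hypokalemia. With the unit corrected, the line agrees with the rest of the protocol.

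The practical risk is low, because the intended value is evident, patient management rests on Section 9.5, and no efficacy endpoint or sample-size figure changes. The conclusion rests on two assumptions: that the extracted text shows the unit as printed, and that Section 9.5 reflects the intended cut. The agreement between Sections 9.5 and 13.5 on both potassium numbers supports the second.

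**What to change.** In Section 13.5, change the unit on the hypokalemia line from meq/ml to mEq/L, so that the event is potassium below 3.0 mEq/L. This matches the hyperkalemia line and the Section 9.5 footnote. Check that the adverse event case report form and any analysis program use the same cut.

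The cost is a one-word correction at the next amendment, with the IRB review that Section 17.4 requires for any amendment. It needs no new data and no change in study conduct.

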13.6 Relatedness of AE or SAE to IP

Using his/her best medical judgment and the available information on the Investigational Product (IP), the Investigator will determine if the AE and or SAE caused the observed symptoms associated with the event.

- **Not related:** Unestablished reasonable causal relationship between the IP and the AE.
- **Unlikely related:** No temporal association or cause of the event has been identified.
- **Possibly related:** There is reasonable evidence to suggest a causal relationship between the drug and adverse event, however there could be other confounders to the AE
- **Related:** There is a causal relationship

13.7 Severity of AEs

The severity of AEs should be documented using the following criteria.

- Mild: symptom does not influence performance. Subject barely notices it
- Moderate: Subject's daily performance is affected. Treatment may be needed.
- Severe: Subject experiences severe discomfort. Treatment necessary

13.8 Outcome of AEs

One of the following outcomes should be documented

- Not resolved: symptom No improvement
- Resolved: Symptoms have improved.
- Resolved with sequelae: Improvement of AE but has retained a pathological condition related to the event.
- Unknown: Subject refused further contact, not known Fatal: Death as a result of AE

13.9 Recording and Reporting of Adverse Events

At follow up visits or when visited by the Visiting nurse, participants should be asked non-leading questions such as “Have you had any issues lately”, “How do you feel”, “Have you made any changes to your medications recently” and “have you had any medical problems that I should know of”. The principal investigator will be notified promptly of any AE or SAEs within 24 hours of the event.

All AE and SAE's should be promptly documented with Subject ID, the serious adverse event term, onset date, relationship to study product, and a brief narrative of the event. The investigator must promptly determine the relationship to study product or causality. Events should be recorded on the Case Report Forms attached as Appendix F. The Investigator should make the SAEs available to the IRB. Any AE or SAE occurring within 30 days of completion of the study should be reported.

14 STATISTICAL CONSIDERATIONS

An open label, descriptive study to evaluate the clinical utility of a novel formulation of furosemide delivered subcutaneously in patients early signs of fluid overload. Binary variables will be presented as percentages; Gaussian continuous variables will be presented as mean \pm standard deviation (SD), while non-Gaussian continuous variables could be presented as median with interquartile range (IQR). There will be no head-to-head comparison of the participants of the study however the study is expected to provide valuable information on the efficacy of this therapy as measured by the primary endpoints which include percentage weight loss, reduction in pro-BNP, re-admission, percentage with extended treatment, percentage of patients with heart

failure related adverse events and survival at 30 days. As already outlined, safety will be reported based on the incidence of the adverse events and percentage of subjects with skin reaction requiring discontinuation. Data will be analyzed for the initial 20 patients in the pilot phase. At the end of the trial, all the 60 subjects (combined pilot and maintenance phase would be analyzed together). A study with 59 evaluable subjects has the power to detect with 95% confidence the presence of events with an incidence of 5% or greater. Failure of such material event to occur in a study with 59 evaluable patients indicates that the incidence of such event is less than 5%.

15 DATA MANAGEMENT PROCEDURES

Clinical study data will be saved on a password protected dedicated drive used for research purposes at the St Elizabeth Medical Center. Home visits by the visiting nurse and clinic visits will be documented on the provided CRF (attached as Appendix G). Participant file will have the following documents related to the patient such as the following (but not limited to): clinician and nurse's notes, laboratory and imaging reports, screening and enrollment log etc. The Investigator's study file will contain the informed consent, protocol/ amendments, CRF, and other appropriate documents and correspondence such as with the IRB and the FDA. The investigator will endeavor to retain clinical study records for at least two years after the last approval of a marketing application in an ICH region; or, until two years after the IND is discontinued and regulatory authorities have been notified. scPharmaceuticals will be notified prior to destroying any clinical study records.

16 STUDY ADMINISTRATION

The Principal Investigator agrees by her participation that the results of this study may be used for submission to national and/or international registration and supervising authorities. If required, these authorities will be provided with the name of the Principal Investigator, their addresses, qualifications and extent of involvement. It is understood that the Principal Investigator is required to provide scPharmaceuticals with all study data, complete reports, and access to all study records. The sc2Wear™ Furosemide Infusor will be returned to scPharmaceuticals at the completion of the study.

Data generated by this study must be available for inspection by the US FDA and other regulatory authorities, by scPharmaceuticals and its designees, and the IRB as appropriate. At a Subject's request, medical information may be given to his or her personal physician or other appropriate medical personnel responsible for his or her welfare. Subject medical information

obtained during the course of this study is confidential and disclosure to third parties other than those noted above is prohibited.

17 ETHICAL AND REGULATORY CONSIDERATIONS

17.1 Ethics and Good Clinical Practice

By signing this protocol, the investigator will ensure adherence to the protocol and to Good Clinical Practice as stated in the following documents.

1. The principles of the “Declaration of Helsinki”
2. ICH Harmonized Tripartite Guidelines for Good Clinical Practice 1996.
3. US 21 Code of Federal Regulations dealing with clinical studies (including parts 312 (IND regulations), 54 (financial disclosure), 50 (informed consent) and 56 (IRB regulations).

17.2 Informed Consent

A written informed consent will be obtained from all participants prior to enrolling in the study. This consent , which is attached as appendix F, will be obtained by the Principal Investigator or designee A copy of the signed consent form will be provided to the Subject

17.3 Confidentiality and HIPAA requirements

Confidentially will be maintained for all the information collected on study participants per the Health Insurance Portability and Accountability Act of 1996 (HIPAA; Pub.L. 104–191, 110 Stat. 1936). Only authorized personnel will have access to subject information collected as part of this study.

17.4 Institutional Review Board/Independent Ethics Committee

This study will only be started when the Institutional Review Board (IRB) approves the protocol. All amendments to the protocol are subject to IRB review and approval

17.5 Monitoring

The study will be monitored by the Principal Investigator to ensure compliance to the study protocol, verify the signing of informed consent by the subjects, and assist the study personnel with

any questions related to the study. Also an institution designated person will have direct access to the study data, informed consent and CRF to ensure consistency and accuracy in data gathering. This designee will have direct access to the Investigator's source documentation in accordance with International Conference on Harmonization Good Clinical Practice (ICH-GCP).

19 APPENDICES

Appendix A. Schedule of Assessments

	Screening	Baseline	Treatment*	First Post Treatment	Second Post Treatment (if applicable)	Post-Treatment Visit
Day	0	0	Daily (3 ± 4 days)	Within 24hrs of last treatment	Within 24hrs of last treatment	30±3days after first dose
Informed Consent	X					
Pregnancy Test*	X					
Training		X				
Medical History		X				
Initial sc2Wear Treatment		X				
Weight		X	X	X	X	X
Height		X				
HF Physical Exam		X	X	X	X	X
NYHA		X		X	X	X
Baseline Labs ^a		X				
Monitoring labs ^b			X	X	X	X
Vitals Signs ^c		X	X	X	X	X
Dyspnea Scale		X	X	X	X	X
Electrolyte correction		X	X			
Injection Site Inspection			X	X	X	X
Current Medication	X	X	X	X	X	X
Adverse Events ^d		X	X	X	X	X

- * To be performed by Steward Home Care and Hospice in accordance with standard practices for homebound heart failure patients
- a. Baseline laboratory panel (Sodium, potassium, Bun, Cr, Mg, pro-BNP, Hemoglobin and Hematocrit)
- b. Monitoring laboratory panel: (sodium, chloride, bicarbonate, potassium, Bun, Cr, Mg)
- c. Vital signs: Blood pressure, heart rate, temperature, respiratory rate
- d. Adverse Events: Major Event: death, hospitalization, MACE (major adverse cardiac event); Minor: ER visit for acute decompensated heart failure (excluding study related visits), admission to SNF or similar inpatient facility

Appendix B: Modified Medical Research Council Dyspnea Scale

Score	Modified Medical Research Council Scale
0	I only get breathless with strenuous exercise.
1	I get short of breath when hurrying on level ground or walking up a slight hill.
2	On level ground, I walk slower than people of the same age because of breathlessness or have to stop for breath when walking at my own pace.
3	I stop for breath after walking about 100 yards or after a few minutes on level ground.
4	I am too breathless to leave the house or I am breathless when dressing

Appendix C: Instructions for Use Manual

Appendix D. Quick Reference Guide (QRG)

Appendix E: Informed Consent Form

Appendix F: Case Report Form (Adverse Events)

Appendix G: Case Report Form (Home Visits)
